# CONFIDENTIAL

interim analysis	An interim analysis is an analysis of clinical study data, separated into treatment groups, that is conducted before the final reporting database is created/locked.	
investigational product (IP)	A pharmaceutical form of an active ingredient or placebo being tested or used as a reference in a clinical trial, including products already on the market when used or assembled (formulated or packaged) in a way different from the authorized form, or marketed products used for an unauthorized indication, or marketed products used to gain further information about the authorized form.	
IRB	Institutional Review Board (IRB), also called Independent Ethics Committee (IEC) or Ethical Review Board (ERB)	
ISS7	Itch Severity Score Over 7 Days	
ІТТ	intention to treat: The principle that asserts that the effect of a treatment policy can be best assessed by evaluating on the basis of the intention to treat a participant (that is, the planned treatment regimen) rather than the actual treatment given. It has the consequence that participant allocated to a treatment group should be followed up, assessed, and analyzed as members of that group irrespective of their compliance to the planned course of treatment.	
IV	intravenous, intravenously	
IWRS	interactive web-response system	
LTBI	latent tuberculosis infection	
MMRM	mixed-effects model of repeated measures	
NONMEM	nonlinear mixed effects modeling	
NSAID	nonsteroidal anti-inflammatory drug	
ΡΑ	posterior-anterior	
participant	Equivalent to Clinical Data Interchange Standards Consortium (CDISC) term "subject," meaning an individual who participates in a clinical trial, either as recipient of an investigational medicinal product or as a control.	
	In this protocol, the term "participant" is used to indicate an individual who participates in a clinical trial, either as a recipient of an investigational medicinal product or as a control. This usage reflects preferences indicated by patient advocates to more accurately reflect the role of people who take part in clinical trials.	
PD	pharmacodynamic	
PK	pharmacokinetic	
PPD	purified protein derivative	
Q2W	every 2 weeks	
RNA	ribonucleic acid	
SAE	serious adverse event	

LY3454738

# CONFIDENTIAL

SAP	statistical analysis plan
screen	The act of determining if an individual meets minimum requirements to become part of a pool of potential candidates for participation in a clinical study.
SoA	Schedule of Activities
study drug	See "study intervention"
study intervention	Any investigational intervention, marketed product, placebo, or medical device intended to be administered to a study participant according to the study protocol
ТВ	tuberculosis
TBL	total bilirubin level
TEAE	Treatment-emergent adverse event: An untoward medical occurrence that emerges during a defined treatment period, having been absent pretreatment, or worsens relative to the pretreatment state, and does not necessarily have to have a causal relationship with this treatment.
TST	tuberculin skin test
UAS7	Urticaria Activity Score Over 7 Days
ULN	upper limit of normal
UPDD	Urticaria Patient Daily Diary
USA	United States of America; also United States
WBC	white blood cell
WOCBP	women of childbearing potential (see Appendix 10.4)

# **10.8.** Appendix 8: Protocol Amendment History

The Protocol Amendment Summary of Changes Table for the current amendment is located directly before the Table of Contents (TOC).

### Amendment A (23 Aug 2019)

This amendment was considered to be nonsubstantial based on the criteria set forth in Article 10(a) of Directive 2001/20/EC of the European Parliament and the Council of the European Union because it neither significantly impacts the safety or physical/mental integrity of participants nor the scientific value of the study.

### **Overall Rationale for the Amendment**

The purpose for the amendment was to provide clarification of the timing of the first post-treatment follow-up visit (Visit 801) relative to the last dosing visit (Visit 15, Week 22).

Section # and Name	Description of Change	Brief Rationale
Section 4.1, Overall Design	Corrected the sentence that describes the interval between the last dosing visit and the first post-treatment follow-up visit. The interval should be written as "6 weeks," not "2 weeks" in Section 4.1.	For accuracy and consistency with information provided in Section 4.2 and in the Schedule of Activities.

### Amendment B (29 Jan 2020)

This amendment is considered to be nonsubstantial based on the criteria set forth in Article 10(a) of Directive 2001/20/EC of the European Parliament and the Council of the European Union because it neither significantly impacts the safety or physical/mental integrity of participants nor the scientific value of the study.

### **Overall Rationale for the Amendment:**

The rationale for the amendment is to mainly address regulatory feedback received in January 2020.

Section # and Name	Description of Change	Brief Rationale
Table 1, Schedule of activities for the screening and treatment periods of Study J1B-MC-FRCF	Added ECG assessments for visits V9, V16, and ETV for the treatment period	Changed per request from the regulatory agency
Section 5.2, Exclusion Criteria	Deleted the following text from criterion [32]: "or during the study"	Changed per request from the regulatory agency

Section # and Name	Description of Change	Brief Rationale
Section 8.1.3.1, Dermatology Life Quality Index	Corrected the scoring classification for DLQI	Corrected an error
Section 8.3.7.2, Allergic Reactions and Hypersensitivity Events and Section 11, References	Added the citation for Sampson et al. 2006	Changed per request from the regulatory agency
Section 10.1.9, Study and Site Start and Closure	Added the "stopping rules" for the study	Changed per request from the regulatory agency

5.6. Bioanalytical and Pharmacokinetic/Pharmacodynamic Methods	
5.7. Safety Analyses	
5.7.1. Extent of Exposure	
5.7.2. Adverse Events	
5.7.2.1. Serious Adverse Event Analyses	27

5.7.2.2	. Other Significant Adverse Events	
5.7.3.	Clinical Laboratory Evaluation	27
5.7.4.	Vital Signs and Other Physical Findings	
5.7.5.	Immunogenicity	
5.7.6.	Special Safety Topics, including Adverse Events of Special	
	Interest	
5.7.6.1	. Abnormal Hepatic Tests	
5.7.6.2	. Renal Function Effects	
5.7.6.3	. Infections	
5.7.6.4	. Allergic Reactions/Hypersensitivities	
5.8. Prot	ocol Deviations	
5.9. Inter	rim Analyses and Data Monitoring	
5.10. Ann	ual Report Analyses	
5.11. Clin	ical Trial Registry Analyses	
6. Referen	nces	
7. Append	lices	

	Table of Contents
Table	Page
Table FRCF.5.1. Outcomes	Description and Derivation of Primary, Secondary and Exploratory Efficacy 16
Table FRCF.5.2. Period 2	Description of Primary, Secondary and Exploratory Efficacy Analyses in 21
Table FRCF.5.3. Pulse Measure	Categorical Criteria for Abnormal Treatment-Emergent Blood Pressure and ment, and Categorical Criteria for Weight Changes for Adults
Table FRCF.5.4 Renal Effects	Common Terminology Criteria for Adverse Events (CTCAE) Related to 31

Table of Contents

	Table of Contents
Figure	Page
Figure FRCF.4.1.	Illustration of study design for Clinical Protocol J1B-MC-FRCF11

Table of Contents			
Appendix		Page	
Appendix 1.	Lilly-Defined MedDRA Preferred Terms for Herpes Zoster		
Appendix 2.	Lilly-Defined MedDRA Preferred Terms for Tuberculosis	40	
Appendix 3.	Lilly-Defined MedDRA Preferred Terms for Potential Opportunistic 43	Infections	

2. Revision History

Statistical Analysis Plan (SAP) Version 2 is based on Protocol J1B-MC-FRCF (c) and was approved prior to unblinding.

SAP Amendment Summary of Changes Table

DOCUMENT HISTORY		
Document	Date	
Amendment A	07-Jul-2020	
Original SAP	05-Mar-2020	

Amendment A

Section # and Name	Description of Change	Brief Rationale
Section 5.2, Sample Size Determination	Updated the effect size assumption for LY3454738 and updated the power.	Clarified per ethics committee feedback.
Section 5.3.1, Analysis Populations	Added definition for Per- Protocol (PPS) population.	Added one more type of analysis populations.
Section 5.3.4.1, Demographics	Added this new subsection to clarify the patient's demographics we want to collect.	Added more details.
Section 5.3.4.2, Baseline Disease Characeteristics	Added this new subsection to clarify the patient's baseline disease activities information we want to collect.	Added more details.
Table FRCF.5.2, Description of Primary, Secondary and Exploratory Efficacy Analyses in Period 2	Added analyses of percent change from baseline for UAS7/ISS7/HSS7 at Week 12. Added analyses on PPS population for some key endpoints. Added the factors in the logistic regression model for DLQI(0,1).	Added more exploratory analyses. Added some analyses on PPS population.
Table FRCF.5.3, Description of Exploratory Efficacy Analyses in Period 3	Changed the analysis method for HSS7 change from baseline from "MMRM" to "Summary Statistics".	Typo correction.
Section 5.7.2, Adverse Events	Clarified the definition for TEAEs.	Minor clarification.

Section # and Name	Description of Change	Brief Rationale
Section 5.7.6.5, Columbia Suicide Severity Rating Scale	Deleted this whole section because this information is not available for this study.	Deleted unnecessary sections.
Section 5.8, Protocol Deviations	Changed the mITT population to PPS population.	Minor clarification.

3. Study Objectives

3.1. Primary Objective

The primary objective of this study is to test the hypothesis that treatment with LY3454738 is superior to placebo in adult participants with CSU, as assessed by the mean change from baseline at Week 12 in weekly Urticaria Activity Score (UAS7), which is the sum of weekly Itch Severity Score (ISS7) and weekly Hives Severity Score (HSS7).

3.2. Secondary Objectives

The secondary objectives of the study are the following:

Objectives	Endpoints
• To compare the efficacy of LY3454738 to placebo as measured by improvement in signs and symptoms of CSU	 Mean change from baseline to Week 12 in ISS7 HSS7
	 Proportion of patients achieving UAS7 ≤6 at Week 12
• To characterize the pharmacokinetics (PK) of LY3454738	• Cmax and AUC

3.3. Exploratory Objectives

Exploratory objectives and endpoints may include the following:

Objectives/Endpoints

- To evaluate signs and symptoms and measures of quality of life at various time points in Period 2 (first 12 week treatment period) and in Period 3 (second 12-week treatment period, after crossover) using the DLQI and the UPDD items.
- To assess the potential development of anti-LY3454738 antibodies and their impact on the safety profile and PK of LY3454738.
- To explore relationships between LY3454738 exposure and select biomarkers and clinical efficacy endpoints.

4. Study Design

4.1. Summary of Study Design

Study J1B-MC-FRCF (FRCF) is a multicenter, randomized, double-blind, placebo-controlled, Phase 2 crossover study to evaluate the efficacy and safety of LY3454738 500 mg given intravenously (IV) every 2 weeks (Q2W) versus placebo IV Q2W in adults with CSU inadequately controlled with H₁-antihistamines.

The study duration will be up to approximately 39 weeks over 4 study periods, as shown below:

Period 1: Screening, lasting up to 35 days before Week 0 (Visit 2, baseline)

Period 2: First 12-week treatment, from Week 0 (Day 1) through Week 12:

• Participants will be randomized in a 3:1 ratio to receive either LY3454738 500 mg IV or placebo IV Q2W

Period 3: Second 12-week treatment (crossover), from Week 12 through Week 24:

- Participants who received LY3454738 500 mg IV in Period 2 will receive placebo IV Q2W in Period 3.
- Participants who received placebo IV in Period 2 will receive LY3454738 500 mg IV Q2W in Period 3.

Period 4: Post-treatment follow-up for approximately 10 weeks.

- Participants will not receive study drug in Period 4.
- The last dose of study drug is given at Week 22, which is 6 weeks before the first post-treatment follow-up visit (Visit 801). Thus, participants will have been withdrawn from study drug for a total of 12 weeks at the last post-treatment follow-up visit (Visit 802).

Approximately 85 patients will be screened to achieve approximately 60 randomized participants. A total of approximately 52 evaluable participants are expected.

Throughout the study, participants will take a second-generation H_1 -antihistamine at a dose specified in approved product labeling. Certain participants may receive rescue therapy as described in Section 6.5.2 in the protocol.

Participants who permanently discontinue the study drug early will undergo early termination procedures, including an early termination visit (ETV) and the post-treatment follow-up visits specified in the Schedule of Activities (SoA) (Section 1.3 in the protocol).

Figure FRCF.4.1 illustrates the study design. The blinding procedure is described in the Protocol.

[figure not shown]

Figure FRCF.4.1. Illustration of study design for Clinical Protocol J1B-MC-FRCF.

Abbreviations: C = crossover visit; D = day; Q2W = every 2 weeks; R = randomization visit; W = study week relative to randomization visit; V = visit.

4.2. Method of Assignment to Treatment

Subjects who meet all criteria for enrollment will be randomized in a 3:1 ratio to double-blind treatment at Visit 2. Assignment to treatment groups will be determined by a computer-generated random sequence using an interactive web-response system (IWRS).

5. A Priori Statistical Methods

5.1. Statistical Hypotheses

The study will compare LY3454738 with placebo in adults with CSU. The primary study objective is to demonstrate superior efficacy of LY3454738 over placebo.

The primary comparison of interest is the mean change of the UAS7 from baseline to Week 12. Secondary comparisons include the mean change of the ISS7 and the HSS7 from baseline to Week 12 as well as the proportion of participants achieving a UAS7 ≤ 6 at Week 12.

Efficacy comparisons will be made regardless of treatment discontinuation and without regard to changes to any background therapies. No adjustments for multiplicity will be made across the efficacy assessments.

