#### **Prohibited Concomitant Medication Use**

- The participant requires treatment with a prohibited medication (Section 6.5.4).
- The participant changes the background H1-antihistamine.

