#### **Other Reasons**

• Unblinding: If an investigator, site personnel performing assessments, or participant is unblinded, the participant must be discontinued from the study drug and continue to post-treatment follow-up. In cases where there are ethical reasons to have the participant continue on study drug, the investigator must obtain specific approval from the sponsor or designee for the participant to continue.

Participants discontinuing from the study drug prematurely for any reason will complete AE and other follow-up procedures as specified in the SoA (Section 1.3), Section 8.2 ("Safety Assessments"), and Section 8.3 ("Adverse Events and Serious Adverse Events"), including ETV **and** post-treatment follow-up visits (V801, V802).

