# 9. Statistical Considerations

# 9.1. Statistical Hypotheses

The study will compare LY3454738 with placebo in adults with CSU. The primary study objective is to demonstrate superior efficacy of LY3454738 over placebo.

The primary comparison of interest is the mean change of the UAS7 from baseline to Week 12. Secondary comparisons include the mean change of the ISS7 and the HSS7 from baseline to Week 12 as well as the proportion of participants achieving a UAS7  $\leq 6$  at Week 12.

Efficacy comparisons will be made regardless of treatment discontinuation and without regard to changes to any background therapies. No adjustments for multiplicity will be made across the efficacy assessments.

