# 9.4.3. Secondary Endpoints

Secondary comparisons of interest are described below. The objective of these secondary endpoints is to demonstrate superiority of LY3454738 over placebo.

# 9.4.3.1. Change from Baseline in ISS7 at Week 12

Change from baseline in ISS7 at Week 12 is the Week 12 ISS7 score minus the baseline ISS7 score. An ANCOVA model similar to the one described for the primary endpoint will be used for analysis of this secondary endpoint.

#### 9.4.3.2. Change from Baseline in HSS7 at Week 12

Change from baseline in HSS7 at Week 12 is the Week 12 HSS7 score minus the baseline HSS7 score. An ANCOVA model similar to the one described for the primary endpoint will be used for analysis of this secondary endpoint.

#### 9.4.3.3. Proportion of Patients with UAS7 ≤6 at Week 12

The proportions of participants who achieve a UAS7 score  $\leq 6$  at Week 12 will be presented for each treatment group. Participants will be classified as nonresponders at Week 12 (that is, did not achieve UAS7  $\leq 6$  at Week 12) if they have a missing UAS7 score at Week 12.

The Cochran-Mantel-Haenszel test stratified by baseline UAS7 (< median versus  $\geq$  median) will be performed to compare the proportions of participants with UAS7  $\leq$ 6 at Week 12 in the LY3454738 group versus placebo.

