5.4. Handling of Dropouts or Missing Data

Missing continuous scores will be imputed using baseline observation carried forward (BOCF) analyses.

The UAS7 score is the sum of the daily UAS scores over 7 days each week. The daily score is the average of 2 results when both entries are made, or it is the single result when only 1 entry is made in a given day. When 1 or more of the daily UAS scores are missing, the following principles will be applied to handle the missing data:

- If a participant has at least 4 nonmissing daily UAS scores within the 7 days prior to the study visit, the UAS7 score is calculated as the sum of the available UAS scores in that week, divided by the number of days that have a nonmissing diary UAS score, multiplied by 7.
- If there are less than 4 nonmissing daily UAS scores within the prior 7 days, then the UAS7 score is missing for the week.

The same principles will be applied to handle the missing data for all of the weekly outcomes.

- Nonresponder imputation (NRI): All participants who discontinue the study or the study treatment at any time for any reason will be defined as nonresponders for the analysis of categorical efficacy variables at discontinuation and subsequent visits.
- Mixed-effects model of repeated measures (MMRM): Continuous variables will be assumed to be missing after discontinuation for which an MMRM analysis will be performed. The model will include treatment, visit, and treatment-by-visit-interaction as fixed categorical effects and baseline and baseline-by-visit-interaction as fixed continuous effects. An unstructured (co)variance structure will be used to model the between- and within-patient errors. If this analysis fails to converge, the heterogeneous autoregressive [ARH(1)], followed by the heterogeneous compound symmetry (CSH), followed by the heterogeneous Toeplitz (TOEPH) will be used. The Kenward-Roger method will be used to estimate the degrees of freedom. Type III tests for the least-squares means (LSM) will be used for the statistical comparison. The LSM difference, standard error, p-value and 100(1-alpha)% CI will also be reported.
- BOCF, as previously stated.

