	leisure, work and school, personal relationships, and treatment. The recall period of this scale is over the "last week." Response categories include "a little," "a lot," and "very much," with corresponding scores of 1, 2, and 3, respectively, and "not at all," or	 Work and school domain 	Sum of questions 7 and 7B (if it is answered), range 0 to 3. Responses of "yes" and "no" on Question 7 are given scores of 3 and 0 respectively. If Question 7 is answered "no" then Question 7b is answered with "a lot", "a little", "not at all" getting scores of 2, 1, 0 respectively.	N/A – partial assessments cannot be saved.
	unanswered ("not relevant") responses scored as 0. Scores range from 0-30	 Personal relationships domain 	Sum of questions 8 and 9, range 0 to 6.	N/A – partial assessments cannot be saved.
	with higher scores indicating greater impairment of quality of life. A DLQI	 Treatment domain 	Question 10, range 0 to 3.	N/A – partial assessments cannot be saved.
	total score of 0 to 1 is considered as having no effect on a patient's	 DLQI total score 	DLQI total score: sum of all six DLQI domain scores, range 0 to 30.	N/A – partial assessments cannot be saved.
	health-related QoL (Hongbo et al. 2005), and a 4-point change from	 Change from baseline in DLQI 	Change from baseline: observed DLQI score – baseline DLQI score	Missing if baseline or observed value is missing.
	baseline is considered as the minimal clinically important difference threshold (Khilji et al. 2002; Basra et al. 2015).	 DLQI 0/1 	Observed DLQI score equals 0 or 1	N/A – partial assessments cannot be saved.

Measure	Variable	Analysis Method	Population (Section 5.3.1)	Comparison/Time Point	Analysis Type
Weekly Urticaria Activity Score	• Change from baseline in UAS7 score at Week 12	ANCOVA using BOCF	mITT; PPS	LY3454738 500-mg vs PBO; Week 12	Primary analysis
(UAS7)	• Percent change from baseline in UAS7 score at Week 12	ANCOVA using BOCF	mITT	LY3454738 500-mg vs PBO; Week 12	Exploratory analysis
	• Change from baseline in UAS7 score by visit (Week 0 through Week 12)	MMRM	mITT	LY3454738 500-mg vs PBO; Week 12	Exploratory analysis
	• Percent change from baseline in UAS7 score by visit (Week 0 through Week 12)	MMRM	mITT	LY3454738 500-mg vs PBO; Week 12	Exploratory analysis
	• Proportion of patients with UAS7 score ≤ 6 at Week 12	Cochran-Mantel-Haenszel test stratified by baseline UAS7 (< median versus ≥ median) using NRI	mITT; PPS	LY3454738 500-mg vs PBO; Week 12	Secondary analysis

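### The SAP promises efficacy comparisons whether or not treatment was stopped, but its nonresponder rule recodes treatment discontinuers on UAS7 ≤6, and no rule gives a discontinuer without Visit 9 a Week 12 score

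*SAP*

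**What the plan says.** **Stated comparison.** SAP 5.1: "Efficacy comparisons will be made regardless of treatment discontinuation and without regard to changes to any background therapies". Protocol 9.1 has the same commitment ("Efficacy comparisons will be made regardless of treatment discontinuation"). Both sections list UAS7 ≤6 among the secondary comparisons.

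**Nonresponder rules for UAS7 ≤6.** SAP 5.4, with the same wording in Protocol 9.4.1.3: "All participants who discontinue the study or the study treatment at any time for any reason will be defined as nonresponders", from the point of discontinuation onward. SAP Table FRCF.5.2 specifies for this endpoint a "Cochran-Mantel-Haenszel test stratified by baseline UAS7 (< median versus ≥ median) using NRI". Protocol 9.4.3.3 gives a different trigger: participants are nonresponders "if they have a missing UAS7 score at Week 12".

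**Continuous endpoints.** The primary UAS7 analysis and the ISS7 and HSS7 analyses are ANCOVAs with BOCF for a missing Week 12 score (SAP 5.5.1 and Table FRCF.5.2). SAP 5.3.2 takes weekly scores from the 7 days before a study visit. SAP 5.4 sets the score to missing when fewer than 4 of those days have an entry.

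**Visits after stopping drug.** SAP 4.1: "Participants who permanently discontinue the study drug early will undergo early termination procedures, including an early termination visit (ETV) and the post-treatment follow-up visits". Protocol Table 2 places V801 and V802 at 4 and 10 weeks after the early termination visit (ETV). It describes the diary as daily, marks a compliance check at V801 and has the device returned at V802. Table 1 has it returned at the ETV only by those who do not enter Period 4.

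**The concern.** A rule that uses stopping treatment as the outcome cannot deliver a comparison made whatever happens to treatment. For UAS7 ≤6 the conflict is in the text itself.

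For the continuous endpoints the difficulty is a gap. Discontinuers are given no Week 12 visit, and nothing says which diary days stand for Week 12. One programmer could take the days before Day 85 as the score; another could find no visit to anchor it to and apply BOCF. The primary result would then depend on a choice the plan does not make, and under the second choice scheduled diary data would be set aside.

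**Working it through.** **1. NRI against the stated comparison.** Visit 9 (Day 85) closes Period 2 and is also the first Period 3 dosing visit. A participant who completes Period 2 dosing, attends Visit 9 and stops drug there can have a full Week 12 diary week.
- SAP 5.1 and Protocol 9.1: the observed response counts.
- Protocol 9.4.3.3: the score is not missing, so this rule does not make the participant a nonresponder.
- SAP 5.4, Protocol 9.4.1.3 and Table FRCF.5.2: nonresponder, because treatment was stopped.

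If all 60 randomized enter mITT at 3:1 (45 and 15), one such recoding moves the responder rate by 1/45 = 2.2 points on drug or 1/15 = 6.7 points on placebo. The documents do not say how often this would happen.

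**2. Diary coverage of Days 78–84.**
- If entries run to V802 (ETV day + 70): ETV + 70 ≥ 85 needs an ETV at Day 15 (Week 2) or later. If V802 is 7 days early, as its window allows, it needs Day 22 (Week 3).
- If entries end at V801 (ETV day + 28): ETV + 28 ≥ 85 needs an ETV at Day 57 (Week 8) or later.
- For ETVs at Weeks 1, 2, 4, 6, 8 and 10, a follow-up visit falls nominally on Week 12 only for Week 2 (V802) and Week 8 (V801). Neither is labelled a Week 12 visit.

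**3. The plan's own power figure.** With 52 evaluable at 3:1 (39 and 13), means 17 and 10 and SD 7, power is 87.7% by the normal approximation and 86.5% by the exact t. This agrees with about 87% in Protocol 9.2 and is close to the more than 87% in SAP 5.2. The figure is not in dispute.

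**4. Illustrative effect on the primary comparison.** Planning values with 45 and 15, a pooled t-test without baseline adjustment, and 60,000 simulated trials per cell. D participants lack a Week 12 score and are split at random between arms. BOCF sets their change to 0; the diary alternative draws it from a normal distribution with SD 7. With an assumed mean change of 10 in both arms:

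| D | Power, BOCF | Power, diaries |
|---|---|---|
| 8 | 67% | 79% |
| 6 | about 73% | about 82–83% |
| 4 | 80% | 86% |

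At D = 8, changing the dropouts' assumed mean change (drug/placebo) gives diary power of 63% for 0/0, 73% for 5/5, 81% for 15/15, 87% for 14/10 and 63% for 5/10. BOCF stays at about 67% throughout.

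For *a* drug and *p* placebo dropouts with mean changes dA and dP, the BOCF estimate minus the diary estimate is (p/15)·dP − (a/45)·dA. With dA = dP = 10:
- 7/1: 0.67 − 1.56 = −0.9
- 6/2: 1.33 − 1.33 = 0
- 5/3: 2.00 − 1.11 = +0.9
- 4/4: 2.67 − 0.89 = +1.8

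Positive values favour drug.

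**The case against.** **The two points rest on different readings.** This stands. If diary days are mapped to Week 12, NRI overrides them and BOCF does not apply. If they are not mapped, BOCF applies and NRI overrides little beyond those who stop at or near Visit 9. A reader might infer that both rules strike the same discontinuers together; the documents do not support that.

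**Nothing makes discontinuation trigger BOCF.** This stands too. A reader might infer that the primary analysis discards discontinuers by rule, but BOCF is tied only to a missing Week 12 score. The ANCOVA point is a gap read literally, not a contradiction.

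**Diary entry to V802 is not written outright.** It is inferred from the daily-completion comment on a row marked at V801, together with device return at V802. Hence the two coverage thresholds above.

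**The sentence in SAP 5.1 may only mean that discontinuers stay in the analysis.** The mITT definition already secures that, and it would not explain a rule that takes stopping treatment as the outcome.

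**The two nonresponder rules can be read as cumulative.** They can. The combined rule still turns on stopping treatment, so the conflict with SAP 5.1 remains.

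**Conclusion.** The conflict between the stated comparison and NRI for UAS7 ≤6 is established from the text and should be fixed. That many discontinuers without Visit 9 would receive BOCF despite existing diary days is an inference. It depends on a literal visit anchor and on how long diary entry continues, and the documents give no discontinuation timing.

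The power figures are illustrative. The documents give no dropout count, arm split or off-drug change, and they do not define evaluable, so 8 participants in mITT without a score is itself an assumption. A reader might infer that using diaries restores power. That is not assured: the range at D = 8 is about 63% to 87% against about 67%, and it falls below BOCF when dropouts return to baseline. Nor is a false-positive problem shown. Under random dropout the null rejection rate favouring drug is about 2.4% with BOCF, against a nominal 2.5%; it would be inflated only if dropout fell disproportionately on placebo. The case rests on the rules not delivering the comparison the plan states.

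Two minor clarifications go with it. Protocol 7.1.1 lists as a possible reason for stopping study drug that "The participant changes the background" antihistamine; through NRI this sits awkwardly with the background-therapy half of the SAP 5.1 sentence. The link is indirect, since NRI acts only if drug is stopped, but the passages should be reconciled. The exploratory MMRM text in SAP 5.4 does not say whether discontinuation means of study or of treatment.

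**What to change.** - In SAP 5.3.2, 5.4 and 5.5.1, define the Week 12 score as the 7 days before Visit 9 or, without a Visit 9, diary Days 78–84, whatever the study-drug status.
- Use that score in the primary ANCOVA, the ISS7 and HSS7 ANCOVAs and the UAS7 ≤6 analysis.
- Apply BOCF or NRI only when that window has fewer than 4 diary days.
- Keep BOCF/NRI for all discontinuers as a sensitivity analysis.
- Align SAP 5.4 and Protocol 9.4.1.3 with Protocol 9.4.3.3, and specify the type of discontinuation in the MMRM text.

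If the sponsor does not intend to use scores after discontinuation, the alternative is to remove the sentence from SAP 5.1 and Protocol 9.1 and say so.

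The cost is wording, one derivation rule and one protocol alignment, with no new data collection. The downsides are that some Week 12 values will reflect time off drug or other CSU therapy, and that an early ETV, non-entry to Period 4 or a sparse diary will still need imputation. For an ETV before about Week 8, days in the window fall after the only scheduled follow-up compliance check, so completeness there is less certain.
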